9.2 Subject Accountability

The number and percent of subjects who were randomized, received investigational product, completed study, discontinued the study (including reason for discontinuing) will be summarized by treatment group and cohort.

Key study dates for the first subject enrolled, last subject enrolled, and last subject's end of study will be presented.

A subject listing and summary noting inclusion in each analysis set will be reviewed for all subjects enrolled. A subject listing noting reason for discontinuation of treatment and reason for discontinuing the study will be reviewed. A list of subjects screened but not enrolled (screen failures) will be reviewed.

A subject listing will be provided for randomization information, randomized treatment and actual treatments.

9.3 Important Protocol Deviations

Important Protocol Deviations (IPDs) categories are defined by the study team before the first subject's initial visit and updated during the IPD reviews throughout the study prior to

database lock. These definitions of IPD categories, subcategory codes, and descriptions will be used during the course of the study. Eligibility deviations are defined in the protocol.

The final list of important protocol deviations (IPDs) will be used to produce the listing of subjects with IPDs in addition, a separate listing of all inclusion and exclusion deviations will be provided.

9.4 Demographic and Baseline Characteristics

Demographic data (i.e. Sex, Ethnicity, Race, Age (Years)) will be summarized using descriptive statistics by treatment group and cohort. If multiple races have been reported for a subject, the subject will be categorized as multiple.

Weight, Height, BMI and Baseline Statin Use (for Cohorts 6 to 9) will be summarized as Baseline Characteristics by treatment group and cohort.

Summary of selected medical history will be provided by system organ class and preferred term for cohorts 6 to 9 by treatment group and cohort.

9.5 Efficacy Analyses

Not applicable for this study.

9.6 Safety Analyses

9.6.1 Adverse Events and Disease-related Events

The Medical Dictionary for Regulatory Activities (MedDRA) version 25.0 or later will be used to code all events categorized as adverse events to a system organ class and a preferred term.

Subject incidence of adverse events will be summarized for all treatment-emergent adverse events, serious adverse events and fatal adverse events by treatment group and cohort during the treatment period.

Severity of adverse events are graded as Mild, Moderate and Severe.

If a subject experienced multiple TEAEs with the same preferred term, this will be counted as separate TEAEs for that treatment under each specific severity recorded.

Summaries of treatment-emergent adverse events, serious adverse events and fatal adverse events during the treatment period will also be tabulated by system organ class, preferred term.

Summary of treatment-emergent adverse events by preferred term and by severity will be tabulated.

SAEs during the follow-up- period will be tabulated by system organ class and preferred term for each treatment group and cohort (cohorts 1-7 only).

Details of each adverse event will be reviewed. Listings of any on-study deaths, serious adverse events (SAE), and events leading to withdrawals of IP or other protocol-required therapies will be reviewed.

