## 6.5 Estimated Study Duration

### 6.5.1 Study Duration for Subjects

Subject participation will vary according to enrollment scheme. The duration of the follow-up period for each cohort was defined based on the simulation results from the population K-PD model describing the Lp(a) response to AMG 890 administration developed based on 57-day GLP repeat-dose cynomolgus monkey toxicology and PK/PD studies (Section 5.2.1). Data suggest that the lengths of study participation proposed will allow plasma Lp(a) levels to return at least to 80% of the baseline levels for each subject after administration across the proposed AMG 890 clinical doses.

For cohorts 1 and 2, planned subject participation will last up to 141 days, including a 28-day screening period prior to investigational product (IP) administration and on-study period (through the end of treatment visit) lasting 113 days.

For cohorts 3 to 7, planned subject participation will last up to 253 days, including a 28-day screening period prior to IP administration and on-study period (through the end of treatment visit) lasting 225 days.

For cohorts 8 and 9, planned subject participation will last up to 393 days, including a 28-day screening period prior to IP administration and on-study period (through the end of study visit) lasting 365 days.

For cohorts 1 to 7, the end of treatment visit will complete the subject's participation in this study unless a follow-up period is required. If there is a clinically significant clinical or laboratory abnormality that requires monitoring, subjects will be followed until resolution of the abnormality or until it is considered stable.

For cohorts 1 to 9, if at the end of treatment visit, the plasma Lp(a) level has not returned to  $\geq 80\%$  of baseline (mean of screening and day 1 predose), the follow-up period will be required.

The end of treatment visit for cohorts 8 and 9 will be the same as the end of study visit (day 365).

Subjects in cohorts 1 and 2 will return to the clinical study site approximately every 2 weeks until the Lp(a) level returns to  $\geq 80\%$  of baseline. Assessments during the follow-up period will include physical examination; vital signs; and collection of blood samples for chemistry, hematology, lipid, Lp(a), and biomarker development. When the protocol amendment 2 is implemented, the follow-up visits will continue approximately monthly, as needed, and will include only Lp(a) monitoring as described below for cohorts 3 to 7.

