## 10.2 General Study Procedures

A signed and dated IRB/IEC approved ICF must be obtained prior to performing any study-specific procedures including discontinuing standard therapy for purposes of this study.

During the study, every effort should be made to perform the study procedures as indicated on the SOA ([Table 4](#) to [Table 9](#)). Every effort should be taken to collect all biomarker and PK samples as described in the SOA. If sample processing/shipment on a weekend/holiday is not logistically feasible for a site, this needs to be documented and will not be considered a protocol deviation.

Subjects will be seen in the clinic for study evaluations. When electrocardiograms (ECGs), vital signs, blood sample collections, and biomarker sample collection occur at the same visit, ECGs and vital signs should be collected before blood samples. The time of blood sample collection must be recorded with the exact time of collection (do not use the time that samples were frozen or any other time point). The study specific manuals provide additional details regarding the requirements for these procedures.

Acceptable deviation windows applicable to visits and sample collections follow:

- $\pm$  5 minutes on the first hour PK assessments on day 1,  $\pm$  10 minutes for the subsequent PK assessments on the same day (dosing day)
- $\pm$  1 hour on days 2 to 4 for PK samples
- $\pm$  1 day on days 7 through 29 for study visits
- $\pm$  3 days from day 43 through the end of treatment visit for study visits of cohorts 1 to 7 and through the end study visit for cohorts 8 and 9

Laboratory samples will be analyzed according to the following:

- At screening, hematology, chemistry, triglycerides, coagulation assessments, FSH, HIV and hepatitis serology tests, eGFR, urine pregnancy test, and drug & cotinine tests will be analyzed at local laboratories.
- At day -1 for cohorts 1 to 5 or day -3 to -1 for cohorts 6 to 9, tests that will be analyzed at local laboratories for eligibility determination will be: alanine aminotransferase (ALT), aspartate aminotransferase (AST); and total bilirubin (TBIL) in the chemistry panel; urine pregnancy test; and drug & cotinine tests. The day -1 tests for cohorts 1 to 5 or day -3 to -1 tests for cohorts 6 to 9 that will be analyzed at a central laboratory will be: hematology, chemistry (including ALT, AST, and TBIL for baseline measurements), eGFR, coagulation assessments, and urinalysis.

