## 12.2 Safety Event Reporting Procedures

### 12.2.1 Adverse Events

#### 12.2.1.1 Reporting Procedures for Adverse Events That do not Meet Serious Criteria

The investigator is responsible for ensuring that all adverse events observed by the investigator or reported by the subject that occur after the first dose of investigational product through the end of treatment visit are reported using the Event eCRF.

The investigator must assign the following adverse event attributes:

- Adverse event diagnosis or syndrome(s), if known (if not known, signs or symptoms),
- **Did the event start prior to the first dose of investigational product,**
- **Assessment of seriousness,**
- Dates of onset and resolution (if resolved),
- Severity,
- Assessment of relatedness to investigational product, protocol required therapies, and/or study mandated procedures
- Action taken, **and**
- **Outcome of event.**

The adverse event grading scale used will be the Amgen Standard Adverse Event Grading Scale: mild (aware of sign or symptom, but easily tolerated), moderate (discomfort enough to cause interference with usual activity), and severe (incapacitating with inability to work or do usual activity). The grading scale used in this study is described in the [Appendix A](#).

The investigator must assess whether the adverse event is possibly related to the investigational product (AMG 890 or placebo). Relatedness means that there are facts or reasons to support a relationship between investigational product and the event.

The investigator must assess whether the adverse event is possibly related to any study mandated activity (eg, administration of investigational product, protocol-required therapies, use of medical device(s) and/or procedure (including any screening procedure(s)).

The investigator is responsible for reviewing laboratory test results and determining whether an abnormal value in an individual study subject represents a clinically significant change from the subject's baseline values. In general, abnormal laboratory findings without clinical significance (based on the Investigator's judgment) are not to be recorded as adverse events. However, laboratory value changes that require treatment

or adjustment in current therapy are considered adverse events. Where applicable and preferentially, clinical sequelae (not the laboratory abnormality) are to be recorded as the adverse event.

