4.2 Subgroups

No subgroup analysis is planned.

5. Definitions

Age at time of enrollment

Subject age in years at time of enrollment will be collected in the clinical database.

AUC_{last}

Area under the concentration-time curve from time zero to the last quantifiable concentration.

AUC_{inf}

Area under concentration-time curve from time 0 extrapolated to infinity.

Baseline

Baseline values for Lp(a) are defined as the mean of screening and day 1 predose. If for any reason only 1 value is available, then that value will be used as baseline.

For any other variable, unless otherwise specified, baseline is defined as the last assessment taken prior to administration of AMG 890 or placebo.

ECG Baseline value

Analysis of ECG is applicable to cohorts 1 to 5 and 8 and 9 only.

Baseline ECG for cohorts 1 to 5 is defined as the mean of the triplicate values measured on Day -1. Baseline ECG for cohorts 8 and 9 is defined as the mean of the 3 triplicate values measured at the Day -3 to -1 dosing pre check visit. If there are any missing values, the mean of the non-missing values will be taken as baseline.

Change from Baseline

Change from baseline is the arithmetic difference between post-baseline and baseline.

Enrollment Date

Enrollment date is defined as the date on which subject was enrolled in the study.

End of Study for the Overall Trial

Defined as when the last subject is assessed or receives an intervention for evaluation in the study i.e. last subject last visit, following any additional parts in the study (e.g. Follow-up period, long term follow-up) as applicable.

End of Study for Individual Subject

Defined as the last date recorded on the End of Study form for an individual subject.

End of Treatment Date

End of Treatment Date for cohort 1 and 2 is the date of Day 113 visit, for Cohort 3 to 7 is the date of Day 225 visit and for cohort 8 and 9 is the date of Day 365 visit.

Fridericia-corrected QT Interval (QTcF)

The Fridericia correction will be calculated from the investigator reported QT (msec) and RR interval (msec), as follows:

$$\text{QTcF} = \text{QT}/\text{RR}^{1/3}$$

Investigational Product

The term investigational product is used in reference to AMG 890 or placebo.

Percentage Change from Baseline

Percentage change from baseline is arithmetic difference between post baseline and baseline divided by baseline values times 100.

Randomization Date

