Randomization date is defined as the date subject was allocated a unique randomization number and assigned to either AMG 890 or placebo group.

Study Day 1

defined as the first day that investigational product is administered to the subject.

Study Day

Post study day 1: study day= (date of event-study day 1) +1

Pre-study day 1: study day= (date of event-study day 1)

Treatment-emergent Adverse Event during Treatment Period

A treatment-emergent adverse event during treatment period is any adverse event starting on or after the first dose of investigational product (as determined by the flag indicating if the adverse event started prior to the first dose or not on the Adverse Events eCRF) and up to and including the End of Treatment Date, **or EOS date for subjects who early discontinue the study during the treatment period.**

Treatment-emergent Serious Adverse Event during Follow-up Period

Subjects in cohorts 1-7 will be followed up for SAE reporting (every 2 weeks for cohorts 1-2 and monthly for cohorts 3-7) if the Lp(a) level has not returned to $\geq 80\%$ of baseline by the end of treatment visit. SAEs during the follow-up period are defined as any serious adverse event **categorized as Adverse Events (AEs) starting on or after first dose of investigational product (as determined by “Did event start before first dose of investigational product” equal to No or missing on the Events eCRF) and starting on or after the end of treatment date and up to and including the end of study date for an individual subject.**

If end of treatment and end of study is same for a subject, then the subject will only have TEAEs for treatment period derived.

For subjects in Cohort 8 and 9 the end of treatment and end of study is same i.e. day 365 so for those cohorts only TEAEs for treatment period will be derived.

6. Analysis Sets

For all analyses, subjects will be analyzed according to the dose and treatment they received, not the dose and treatment to which they were randomized.

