8.4 Detection of Bias

Any source that may introduce bias in the analysis e.g. important protocol deviations, imbalance in baseline characteristics among treatment groups, subject dropout for study or treatment related reasons, nonrandom or informative censoring will be noted in the clinical study report.

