9.1 General Considerations

Descriptive statistics will be provided for selected demographics, adverse events, vital signs, ECG and selected laboratory measurements. Descriptive statistics on continuous measurements will include means, medians, standard deviations, and ranges, while categorical data will be summarized using frequency counts and percentages. Data will be presented and summarized by treatment group and cohort at each scheduled time point. Graphical summaries of the data may also be presented.

Data for subjects receiving placebo will be combined across cohorts 1 to 5 and separately across cohorts 6 to 9.

When data are summarized by time, the values recorded against the scheduled time points listed in the protocol will be used. When assessing minimum/maximum increases or decreases over the study, all assessments, including unscheduled assessments will be used. Unless stated otherwise in the statistical analysis plan, the data analysis will be conducted using subjects in the safety analysis set. For statistical analyses comparing change from baseline, only subjects with both baseline and at least one post-baseline assessment will be included.

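### Crude TEAE incidence is tabulated over 113, 225 or 365 days by cohort beside placebo pools that mix these windows, so later-arising events are not compared like for like

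*SAP*

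**What the plan says.** TEAE subject incidence is a primary endpoint (Protocol 13.1.1.1; SAP 2.1). SAP 9.6.1 tabulates it for all TEAEs, "serious adverse events and fatal adverse events by treatment group and cohort during the treatment period", and SAP 9.1 reports categorical data as counts and percentages. Protocol 13.5.2.1.1 has the percentages looked at both within and across dose cohorts.

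SAP Section 5 counts a TEAE "up to and including the End of Treatment Date", or to the end of study date after early discontinuation. It also fixes that date by cohort: "End of Treatment Date for cohort 1 and 2 is the date of Day 113 visit, for Cohort 3 to 7" it is the Day 225 visit, and for cohorts 8 and 9 the Day 365 visit.

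On placebo, SAP 9.1 says: "Data for subjects receiving placebo will be combined across cohorts 1 to 5 and separately across cohorts 6 to 9". Protocol 13.5.1 agrees. The Protocol Synopsis instead pools placebo over all cohorts. That is a separate inconsistency to reconcile, and windows mix either way.

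The unequal windows are deliberate. Protocol 6.5.1 expects that "the lengths of study participation proposed will allow plasma Lp(a) levels to return at least to 80% of the baseline levels".

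Neither document plans an adverse event table over a common window. The follow-up table in SAP 9.6.1 covers only serious events in cohorts 1-7, so it does not equalize the windows.

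**The concern.** Cumulative incidence cannot fall as the window lengthens. A cohort observed for 113 days therefore has less opportunity to show an event than one observed for 225 or 365 days. No cohort's window matches the mix in its placebo column.

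Within each Lp(a) stratum the window lengthens with dose. In cohorts 1-5 it is 113 days for 3 and 9 mg and 225 days for 30, 75 and 225 mg. In cohorts 6-9 it is 225 days for 9 and 75 mg and 365 days for 225 and 675 mg. For events that continue to arise, the low doses can look better than placebo and the high doses worse with no drug effect.

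This matters most for late events in cohorts 8 and 9. Protocol 5.5.1 says cohort 9 is partly meant to supply safety information under longer Lp(a) suppression.

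**Working it through.** **Plan's own figures.** The chance of at least one event is 1 - (1 - p)^n.
- n = 6, p = 0.20: 1 - 0.8^6 = 73.8% (stated 74%).
- n = 10, p = 0.20: 1 - 0.8^10 = 89.3% (stated 89%).
- Active subjects in Table 1 sum to 60; at p = 0.05, 1 - 0.95^60 = 95.4% (stated 95%).

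All three reproduce. None carries a time window.

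**Inputs.** Windows are from SAP Section 5 and planned numbers from Table 1. Active subjects per cohort are 6 in cohorts 1-5, 8 and 9, and 9 in cohorts 6 and 7. The placebo pool for cohorts 1-5 has 4 subjects at 113 days and 6 at 225. The pool for cohorts 6-9 has 6 at 225 and 4 at 365. Replacements (Protocol 6.4) or extra cohort 9 subjects (Protocol 8.1) could change these.

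**Assumptions.** No drug effect and full follow-up. The 20% is borrowed from the sample-size text and is not a background rate, so two anchor days are shown.

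**Formulas.** rate = -ln(1 - p)/anchor day; I(d) = 1 - exp(-rate × d). Placebo 1-5 = 0.4·I(113) + 0.6·I(225). Placebo 6-9 = 0.6·I(225) + 0.4·I(365).

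**Constant rate.**

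| Assumption | I(113), I(225), I(365) | Placebo 1-5, 6-9 |
|---|---|---|
| 20% by day 225 | 10.6%, 20.0%, 30.4% | 16.2%, 24.1% |
| 20% by day 113 | 20.0%, 35.9%, 51.4% | 29.5%, 42.1% |

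Cohort minus its placebo pool, in percentage points:

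| Assumption | Cohorts 1-2 | 3-5 | 6-7 | 8-9 |
|---|---|---|---|---|
| 5% by day 225 | -1.5 | +1.0 | -1.2 | +1.8 |
| 20% by day 225 | -5.6 | +3.8 | -4.1 | +6.2 |
| 20% by day 113 | -9.5 | +6.3 | -6.2 | +9.3 |
| 20% by day 225, half the cumulative hazard at dosing | -2.7 | +1.8 | -2.1 | +3.2 |
| All events early | 0 | 0 | 0 | 0 |

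Multiplied by the active number per cohort, the 20%-by-day-225 row is -0.34, +0.23, -0.37 and +0.37 subject. Standard errors against 10 placebo subjects are about 17, 20, 19 and 23 points. For 20% by day 113 the gaps are 0.4 to 0.6 subject, with standard errors of 22 to 26 points.

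**Largest constant-rate gaps.**
- Cohorts 1-5: I(225) - I(113) is greatest when rate = ln(225/113)/112 = 0.00615 per day, about 50% by day 113. The difference is 0.248. Multiplying by -0.6 and +0.4 gives -14.9 points (cohorts 1-2) and +9.9 points (cohorts 3-5), at most 6 × 0.149 = 0.89 subject, with standard errors of 23 to 25 points.
- Cohorts 6-9: I(365) - I(225) is greatest when rate = ln(365/225)/140 = 0.00346 per day, about 32% by day 113. The difference is 0.176. Multiplying by -0.4 and +0.6 gives about -7.0 points (cohorts 6-7) and +10.6 points (cohorts 8-9), 0.63 subject each, with standard errors of about 23 to 24 points.

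**Balance of pooled comparisons.** Mean planned window in cohorts 1-5: active (12×113 + 18×225)/30 = 180.2 days; placebo (4×113 + 6×225)/10 = 180.2 days. In cohorts 6-9: active (18×225 + 12×365)/30 = 281.0 days; placebo (6×225 + 4×365)/10 = 281.0 days. The 3:1 allocation in every cohort gives the two arms the same mix of windows.

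**Common window.** Cut at day 113, every column expects the same incidence under no drug effect: 10.6% at 20% by day 225.

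**The case against.** The strongest reply is that nothing is decided on these percentages. The tables are descriptive, the gap is under one subject per cohort, and sampling error is larger. The windows are stated openly. SAP 8.4 undertakes that "Any source that may introduce bias in the analysis" will be noted in the report, and its examples are not a closed list. SAP 9.6.1 also has each event reviewed, and in cohorts this small that carries much of the safety reading. The sizes rest on an assumed constant rate after one dose. In cohorts 3-5 scheduled visits thin from ten between days 7 and 113 to three more by day 225 (Protocol Table 5), so reporting need not be constant.

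Most of this stands, and it limits the point to how cohort percentages are read. It does not remove the mismatch. A general promise to note bias and a set of event listings give no like-for-like comparison. Unlike sampling error, this effect has a known direction, and table layout can remove it.

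A reader might infer more than the documents support:
- *That dose escalation is compromised.* Escalation rests on data through day 15 (Protocol 9.2.4.1), which lies inside every window.
- *That active versus placebo is biased overall.* Pooled within a stratum, the windows balance.
- *That the early risks are misreported.* Injection site and hypersensitivity reactions (Protocol 5.3) are not affected where they occur in the first weeks.
- *That the full-window table is wrong.* Its windows were set to cover Lp(a) recovery, and it is a legitimate summary.

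**Conclusion.** The mismatch is real and its direction is clear for later-arising events: with no drug effect, cohorts 1-2 and 6-7 are expected below their placebo pool and cohorts 3-5 and 8-9 above it. High confidence covers that much and not the size, which depends on a background rate and event timing that the documents do not give. At the illustrative 20% by day 225, the gaps run from 3.8 to 6.2 points in size. At any constant rate they cannot exceed about 15 points in cohorts 1-5 or 11 points in cohorts 6-9. This is a low-cost improvement to the reading of a primary endpoint and no threat to the trial's conclusions.

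**What to change.** In SAP 9.6.1, keep the full-window table with equal standing and add:

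1. TEAE subject incidence with onset through day 113, or through the end of treatment or end of study date if earlier, for all cohorts and both placebo pools. Day 113 is the longest shared window because non-serious events "that occur after the first dose of investigational product through the end of treatment visit are reported using the Event eCRF". The earlier-date rule is needed because visits may move by plus or minus "3 days from day 43 through the end of treatment visit for study visits of cohorts 1 to 7".
2. A footnote to the full-window table: *Treatment periods differ by cohort (113, 225 or 365 days); percentages are not directly comparable between cohorts with different windows or with the pooled placebo columns.*

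A useful but optional supplement is a day-225 table for cohorts 3-9, with placebo from those cohorts only: 6 subjects from cohorts 3-5 and 10 from cohorts 6-9.

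An exposure-adjusted rate is not a safe substitute. It removes the gap only under a constant hazard. If 20% of every cohort had an event right after dosing, the rates would be 0.2/(0.8×113/365) = 0.81, 0.2/(0.8×225/365) = 0.41 and 0.2/0.8 = 0.25 per subject-year, a false 3.2-fold fall from the shortest to the longest window.

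The cost is SAP wording, a footnote and one or two tables from onset dates already collected. Events after day 113 appear only in the full-window table or the optional day-225 table, and the latter leaves 6 rather than 10 placebo subjects beside cohorts 3-5. Cohorts will still differ in Lp(a) stratum and statin use, and cohort 9 in its wider age, BMI and diabetes criteria.

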### **13. STATISTICAL CONSIDERATIONS**

#### **13.1 Study Endpoints, Analysis Sets, and Covariates**

##### **13.1.1 Study Endpoints**

###### **13.1.1.1 Primary Endpoints**

- Subject incidence of treatment-emergent adverse events
- Safety laboratory analytes, vital signs, and electrocardiograms (ECGs)

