**13.5.2 Primary Endpoint(s)**

**13.5.2.1 Safety Endpoint(s)**

**13.5.2.1.1 Adverse Events**

All subjects who receive a dose of AMG 890 or placebo in the safety analysis set will be included in the analysis of the primary endpoints. Subject incidence of all treatment-emergent adverse events will be tabulated by system organ class and preferred term according to the medical dictionary for regulatory activities (MedDRA) terminology. Tables of fatal adverse events, serious adverse events, adverse events leading to withdrawal from IP or other protocol-required therapies, and significant treatment emergent adverse events will also be provided if observed. The number and percentage of subjects reporting adverse events will be evaluated for each dose cohort and across dose cohorts.

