3.2 Sample Size

The sample size is based on practical considerations. Approximately █ subjects will be enrolled. With at least 6 subjects receiving AMG 890 in each cohort, there is at least a 74% chance of detecting an adverse event with a true incidence of 20% within each cohort. With at least 10 subjects receiving both AMG 890 and statin, there is at least a 89% chance of detecting an adverse event with a true AE incidence rate of 20%. With █ subjects receiving AMG 890 there is a 95% chance of detecting an adverse event with a true incidence of 5%.

4. Covariates and Subgroups

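### The adverse-event severity table can count one subject under several grades of the same term, so its rows need not match subject incidence or show worst grade

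*SAP*

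**What the plan says.** The primary endpoint in Protocol 13.1.1.1 is "Subject incidence of treatment-emergent adverse events", together with laboratory, vital-sign and ECG data. Protocol 13.5.2.1.1 keeps the same unit: "The number and percentage of subjects reporting adverse events will be evaluated for each dose cohort and across dose cohorts". SAP 9.6.1 also begins with subjects: "Subject incidence of adverse events will be summarized for all treatment-emergent adverse events".

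The same SAP section then turns to severity. It states "Severity of adverse events are graded as Mild, Moderate and Severe" and gives a counting rule: "If a subject experienced multiple TEAEs with the same preferred term", then "this will be counted as separate TEAEs for that treatment under each specific severity recorded". The table that the rule feeds is described as "Summary of treatment-emergent adverse events by preferred term and by severity will be tabulated".

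Neither document contains a worst-grade or maximum-severity rule for adverse events. SAP section 10, which lists departures from the protocol's analyses, does not mention severity counting. Elsewhere the SAP does take one extreme value per subject: section 9.6.5 classifies each subject by maximum QTcF change and maximum QTcF value.

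**The concern.** A severity table is normally read as the number of subjects whose worst experience of a term was mild, moderate or severe. Read that way, its rows partition the subjects who had the term and add up to the subject incidence. Under the SAP's rule a subject with mild and later moderate headache appears in both rows. The rows then overlap, and the count of subjects at moderate or worse cannot be obtained by adding Moderate and Severe.

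The unit is also unsettled. The wording could mean one count per subject per grade, or a count of every event. Two programmers could produce different tables from the same sentence. At stake is a clear reading of tolerability by dose in cohorts with 6 or 9 active subjects, where one subject moves a percentage by 16.7 or 11.1 points.

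**Working it through.** The plan states no figure for the severity table, so there is none to reproduce. The check is a direct count under the stated rule.

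**Inputs**
- Three severity grades (SAP 9.6.1), so one subject can fill up to three rows of one term.
- Active cohort sizes: 6 in cohorts 1 to 5, 8 and 9; 9 in cohorts 6 and 7 (SAP Table 1). SAP 3.2 also works with 6: "With at least 6 subjects receiving AMG 890 in each cohort, there is at least a 74% chance of detecting an adverse event" at a true incidence of 20%. That figure checks: 1 − 0.8^6 = 0.738.
- Placebo is pooled over cohorts 1 to 5 and separately over cohorts 6 to 9 (SAP 9.1), giving 5 × 2 = 10 and 3 + 3 + 2 + 2 = 10 subjects.
- The number of subjects with one term at more than one grade is not given. Values below are assumptions.

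**Row sum for one preferred term.** Let k be the subjects with the term, m those with it at exactly two grades, and t those with it at all three. Counting one entry per subject per grade:

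sum of severity rows = k + m + 2t; sum under maximum severity = k.

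| Active subjects | k | m | t | Subject incidence | Row sum, SAP rule |
|---|---|---|---|---|---|
| 6 | 2 | 0 | 0 | 33.3% | 33.3% |
| 6 | 2 | 1 | 0 | 33.3% | 50.0% |
| 6 | 3 | 1 | 0 | 50.0% | 66.7% |
| 6 | 3 | 2 | 0 | 50.0% | 83.3% |
| 6 | 3 | 1 | 1 | 50.0% | 100.0% |
| 9 | 3 | 1 | 0 | 33.3% | 44.4% |

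The first line shows that the excess is conditional: with no subject at two grades, the rows agree with incidence.

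**Can worst grade be recovered?** Take the third line (6 subjects, k = 3, m = 1) with rows Mild 2, Moderate 1, Severe 1. Two different sets of subjects give these rows:
- One subject mild and moderate, one mild, one severe. Worst grades: Mild 1, Moderate 1, Severe 1. Moderate or worse: 2/6 = 33.3%.
- One subject moderate and severe, two mild. Worst grades: Mild 2, Moderate 0, Severe 1. Moderate or worse: 1/6 = 16.7%.

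The incidence table shows 3/6 in both cases, so it does not settle which one occurred.

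**Unit.** One subject with three mild events of a term adds 1 to the Mild row if subjects are counted per grade, and 3 if events are counted.

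**How often.** Suppose a share q of affected subjects has the term at exactly two grades. The expected row sum is then (1 + q) times the incidence: 1.00, 1.10 and 1.30 times for q = 0, 0.10 and 0.30. For a term with 20% incidence, the chance of any excess in a cohort of n is 1 − (1 − 0.2q)^n. With n = 6 this is 0%, 11.4% and 31.0%; with n = 9 it is 0%, 16.6% and 42.7%.

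**Active against placebo.** If each subject has probability r of such a duplicate, a column of n expects n·r extra entries, or n·r/n = r as a proportion. With 20% incidence and q = 0.10, r = 0.02: 0.12/6 and 0.20/10 are both 2.0 percentage points. Column size drops out.

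**The case against.** The strongest case for leaving the text alone is that the rule is explicit and prespecified, keeps recurrences visible, and touches only an additional descriptive table. The SAP plans no total across severity rows, and each row is true as it stands. Subject incidence is tabulated separately, overall and by system organ class and preferred term. If subjects are counted per grade, the Severe row is the same under either rule; only the lower rows gain entries. Protocol 12.2.1.1 records severity as one attribute of each adverse event, so duplicates probably need separately recorded recurrences. With 6 to 9 active subjects per cohort, individual events can be reviewed directly. All of this stands, and it keeps the point small. It does not settle the unit, and it does not make the Mild and Moderate rows readable by worst grade.

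A reader might infer more: that duplicates inflate small active cohorts more than pooled placebo and so mimic a drug effect. One duplicate does add 1/6 = 16.7 points in a cohort of 6 and 1/10 = 10.0 points in pooled placebo, a gap of 6.7 points. But one duplicate in 6 subjects and one in 10 are different per-subject rates. At equal rates the expected rise is the same in both columns. The 6.7 points reflect only the sizes of the denominators: a single event in one subject per column shows the same gap under maximum-severity counting. Against 9 active subjects the gap is 1/9 − 1/10 = 1.1 points. Cohorts also differ in length of follow-up, which could change recurrence rates. The documents give no such rates, and longer follow-up can raise subject incidence as well.

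**Conclusion.** The point holds as a minor, cheaply corrected weakness. Under SAP 9.6.1 the preferred-term-by-severity rows can exceed subject incidence by m + 2t subject entries. The table cannot in general give the number of subjects by worst grade, and its unit is not stated. In the central example this means 4 entries against 3 subjects in a cohort of 6 (66.7% against 50.0%).

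The size depends on how many subjects have one term at two or more grades. The documents do not say, and the effect is nil if there are none. The values q = 0 to 0.30 are assumptions.

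Three larger conclusions are not supported. The primary endpoint is not distorted, because the incidence tables count subjects. Dose decisions are not affected, because Protocol Table 3 rests on individual reactions and the subjects who have them, not on this table. The rule creates no systematic disadvantage for active cohorts against placebo.

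**What to change.** Replace the counting sentence in SAP 9.6.1 with a rule of this kind: in the summary by preferred term and severity, a subject with more than one TEAE of the same preferred term is counted once, at the maximum severity recorded; the same rule applies to any severity summary produced by system organ class or overall. If event counts are wanted, put them in a separate column labelled as events. Keep every individual event in the listing.

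The severity rows then sum to k, the subject incidence of the term: 3/6 (50.0%) in the example. The change costs one SAP sentence and a small programming change, with no change to data collection. The downside is that lower-grade repeats appear only in the listing or the event-count column.
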